
A total of 120 participants will be recruited with 40 participants per group. The 40 participants per group are based on recently performed studies related to text messaging and sleep health. Participants will be randomly assigned to one of three groups. The three groups will consist of a control group in which no intervention will be performed, a one-time educational group that will watch a sleep hygiene video on behavior changes related to healthy sleep, and the third group will get the one-time educational video plus daily automated text messages reinforcing education learned in the video.

Following the initial meeting with the PI, all participants will wear the sleep tracker on their wrist for 2 weeks to collect preliminary data and then 4 additional weeks following their intervention for a total of 6 weeks. The sleep tracker will monitor the physiological markers of sleep provided by wearable technology on sleep efficiency, time in bed, time actually sleeping, sleep midpoint, and time spent at each stage of sleep. At the end of the 6-week study period, the PI and/or student researcher(s) will again meet with each participant. The participant will again complete the following questionnaires: Sleep diary, Epworth Sleepiness Scale, Pittsburgh Sleep Quality Index, Sleep Hygiene Index, Perceived Stress Scale, and Numeric Pain Rating Scale. Anthropometric data collection and vital signs will be reassessed. Pre/post measurements will be compared and data analyses will be conducted using a 2x2 mixed factorial repeated measures ANOVA test.

Assessing overall sleep health is relatively new and therefore there is no established gold standard, however the Ru-SATED questionnaire (Table 1) has been shown to be a reliable and valid measure of sleep health(26). We will use this in combination of objective data from the FitBit device to measure sleep health. Each sleep health domain will be dichotomized using the cut-off points in Table 1 with 0 = poor sleep health and 1 = good sleep health. The domains will be summed to create the composite sleep health score ranging from 0 - 6 with a higher score indicating better sleep health.

Table 1 Sleep Health Composite			
Sleep health domain	Source	Operational definition	Cut-off for good sleep health
Regularity	FitBit	Standard deviation of sleep midpoint, which is calculated as [sleep onset + (wake time – sleep onset/2)]	<60 min

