Satisfaction	Sleep Diary	The sleep diary includes an item to rate “restedness upon awakening” with 0 = “not at all”, 1 = “somewhat”, 2 = “moderately”, 3 = “quite a bit”, and 4 = “extremely”. Satisfaction will be operationalized as the average “restedness” score	Average of ≥ 3
Alertness	Epworth Sleepiness Scale	Epworth Sleepiness Scale which consists of 8-items of various activities (ie. sitting and reading, watching TV, etc) answered using a 4-point Likert Scale with 0 = “would never nod off” to 3 = “high chance of nodding off”	≤ 10
Timing	FitBit	Average sleep midpoint	2am-4am
Efficiency	FitBit	Average total minutes of sleep divided by time in bed multiplied by 100	>85%
Duration	FitBit	Average total minutes of sleep	6-8 hours

Table 1: Sleep Health Composite

[figure not shown]

Figure 1: Study design for Specific Aim 1.

Specific Aim 2: Assess the ability of daily automated text messaging in CDOA to serve as an effective augmentation for sleep hygiene education. Several research studies have shown that a one-time sleep hygiene education session have improved sleep health in younger adults and working individuals(4, 27). With the promising results of a one-time education on short term progress, we want to test if longer-term reminders outside the initial training would provide even more sustainable results. The expansion of smartphone technology opens up an opportunity to reinforce the initial education with continual reminders of good sleep habits. A recent survey demonstrated that 86% of Americans over 50 utilize text messaging(28). In addition, one study showed text messaging significantly improved exercise rates in older adults(25). For this reason, we want to explore using automated text messaging for sleep hygiene education. *We hypothesize that automated text messaging will enhance the treatment effect of a one-time educational session on sleep health in CDOA.*

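### The sleep-midpoint formula printed in Table 1 works out to wake time + onset/2, which is not a midpoint; applied as written, it would misscore Regularity for some participants and, by inference, Timing

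*Protocol*

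**What the plan says.** Table 1 (Sleep Health Composite), Regularity row, takes its data from the FitBit and defines the domain as "Standard deviation of sleep midpoint, which is calculated as [sleep onset + (wake time – sleep onset/2", followed by the closing round and square brackets. Good sleep health is an SD below 60 min. The Timing row is defined only as "Average sleep midpoint", with a good range of 02:00 to 04:00 and no formula of its own.

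The paragraph before Table 1 makes these rows the scoring rule: "Each sleep health domain will be dichotomized using the cut-off points in Table 1 with 0 = poor sleep health and 1 = good sleep health". It then says: "The domains will be summed to create the composite sleep health score ranging from 0 - 6".

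The description of the sleep tracker also lists the midpoint among the measures it monitors: "sleep efficiency, time in bed, time actually sleeping, sleep midpoint, and time spent at each stage of sleep". Neither document gives another midpoint formula or a rule for coding clock times that cross midnight.

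**The concern.** The inner bracket closes in the wrong place. The division by 2 applies to onset alone instead of to the difference between wake time and onset, so the result is not a midpoint. It is not a stable clock time either: it changes with the zero point used to code time, whereas the true midpoint is the same on any continuous scale.

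The formula stands in an operational definition, so an analyst who follows the Protocol to the letter would compute the wrong quantity and compare it with cut-offs meant for a midpoint. Regularity is affected directly. Timing is affected only by inference, because the formula is printed in the Regularity row alone. The other four domains do not use the midpoint, so at most two of the six composite points are exposed.

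**Working it through.** **Inputs.** From Table 1: the printed formula, the Regularity cut-off (SD below 60 min) and the Timing range (02:00–04:00). The documents give no sleep-time distributions, so the onset and wake SDs and correlations below are assumptions.

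**Algebra.** Let o = onset and w = wake time, in signed hours from midnight, and let d = w − o.

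- Printed: P = o + (w − o/2) = w + o/2
- True midpoint: T = o + (w − o)/2 = (o + w)/2
- Difference: P − T = w/2

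Coded in hours from noon, the printed formula gives (w + 12) + (o + 12)/2, which is clock time P + 6 h. On a raw 24-hour clock with onset before midnight it gives w + (o + 24)/2 = P + 12 h.

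**Timing, worked nights** (if the printed formula is used there)

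| Sleep period | True midpoint | Printed, signed hours | Printed, hours from noon | Printed, raw 24-hour |
|---|---|---|---|---|
| 23:00–07:00 | 03:00, good | 7 − 0.5 = 6.5, 06:30, poor | 12:30, poor | 18:30, poor |
| 22:00–04:30 | 01:15, poor | 4.5 − 1 = 3.5, 03:30, good | 09:30, poor | 15:30, poor |
| 01:00–09:00 | 05:00, poor | 9 + 0.5 = 9.5, 09:30, poor | 15:30, poor | 09:30, poor |

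The first row loses the point wrongly, the second gains it wrongly under one coding, and the third keeps its class.

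**Timing, general result.** Take a sleep period over 4 h, onset after noon, and T between 2 and 4.

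- *Signed hours.* If P were also between 2 and 4, then w/2 = P − T ≤ 2, so w ≤ 4. But then T = w − d/2 < 4 − 2 = 2, a contradiction. So P > 4.
- *Other codings.* Since P = 2T − o/2, T ≤ 4 and o > −12, P < 8 + 6 = 14. A good score would need P between 20 and 22 (hours from noon) or between 14 and 16 (raw clock, onset before midnight), and neither is possible. On the raw clock with onset after midnight the value is P itself, which exceeds 4 and is at most 8.

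So no such true midpoint is scored good under any of the three codings. A one-minute grid (onset 20:00–03:00, wake 01:00–12:00, sleep period over 4 h) agrees. Of 212,940 clock-time combinations, all 72,360 that are truly good score poor in each coding. Another 24,120 that are truly poor score good with signed hours, and none do in the other two codings. These are counts of combinations, not of people.

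**Regularity.** For night-to-night SDs so and sw with correlation r, on any continuous time scale:

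- True variance = (so² + sw² + 2·r·so·sw)/4
- Printed variance = sw² + so²/4 + r·so·sw
- Printed minus true = 0.75·sw² + 0.5·r·so·sw

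| Assumed so / sw (min), r | True SD | Printed SD | Class |
|---|---|---|---|
| 50 / 50, 0.5 | √1875 = 43.3 | √4375 = 66.1 | good becomes poor |
| 50 / 50, 0 | √1250 = 35.4 | √3125 = 55.9 | good under both |
| 75 / 75, 0.5 | √4218.75 = 65.0 | √9843.75 = 99.2 | poor under both |

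With equal SDs and r from 0 to 0.8, the printed SD is 1.51 to 1.58 times the true one. True SDs from about 38–40 min (60/1.58 to 60/1.51) up to 60 min therefore move from good to poor.

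**The case against.** The intended formula is plain from the context. The cell itself names a midpoint, and a 02:00–04:00 range makes sense only for a true one. Literal use would also show itself quickly: a 23:00–07:00 sleeper would get a midpoint half an hour before waking in one coding and hours after waking in the other two. An error that visible may well be caught before any data are scored.

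The device offers another way round it. The Protocol lists the midpoint among the "physiological markers of sleep provided by wearable technology on sleep efficiency, time in bed, time actually sleeping, sleep midpoint", and if the value is read from the FitBit no score changes. Against that, the Regularity row says the midpoint is calculated, so the source is open.

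Timing is an inference, the Regularity SDs are assumed, and the grid counts say nothing about how common any pattern is. The same rule would apply before and after and in every arm, so no bias between arms is shown. The SAP's Data Analysis section plans paired tests on tracker data but does not name the composite.

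All of this stands. It limits the likely harm, but it does not make the printed definition correct or say which quantity will be used.

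**Conclusion.** The concern holds. That the printed expression equals wake + onset/2 is exact and needs no assumption. The consequences are conditional on the formula being coded as printed, and nothing in the documents shows that it was.

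Under that condition, Regularity changes class for some participants and not for others, depending on their night-to-night variability. If Timing uses the same formula, every participant with a sleep period over 4 h, onset after noon and a true midpoint in the good range loses that point. Some earlier sleepers gain it wrongly when time is coded in signed hours from midnight. If the midpoint comes from the device or the intended formula is used, only the text is wrong. This should be fixed because it is a scoring definition that cannot be followed as written; distorted results have not been shown.

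**What to change.** In Table 1, replace the expression with: sleep midpoint = sleep onset + (wake time − sleep onset)/2, computed on a continuous time scale that does not break at midnight. Signed hours from midnight and hours from noon both serve and give the same midpoint. State that this definition applies to both Regularity and Timing, and whether the midpoint is taken from the device or computed from onset and wake time.

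Then check the scoring code, and rescore only data that were scored with the printed formula. The cost is a one-line correction, a sentence or two on scope and source, and a short code check.

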Experimental design: Following anthropometric data collection and vital signs, the participants will be randomly assigned to one of three groups (Figure 2). The third group, a one-time education plus automated text messaging, will receive daily automated text messages scheduled for 8:00 pm every evening. The text messages will include a variety of sleep hygiene behavioral tips for the participant to try (Table 2). The participants will receive the text messages for a total of 4 weeks. The control group and the one-time educational group will not receive any intervention during this time frame. Following the 4 weeks, PI and student researcher(s) will meet again with all participants to collect the same data that was collected at the initial visit. Each participant will have a total of 2 sessions to complete with each session taking approximately 45-60 minutes to complete.

[figure not shown]

Figure 2: Study design for Specific Aim 2.

Day	Daily Text
1 & 16	Go to sleep and wake up at the same time every day. This will help set your natural biological clock.
2 & 17	Exposure to bright natural light when you first wake up is also helpful to set your natural biological clock.
3 & 18	Use your bed for only sleep and sexual activity to help train your brain that if you are in your bed, you should be sleeping. Do not eat, work, or watch TV in bed. Do these activities outside of the bedroom.
4 & 19	Leave bed if unable to fall asleep within 20 minutes and return when sleepy. If unable to leave the bed due to limited mobility or safety concerns, do something relaxing (ie, relaxation techniques) until sleepy and able to fall to sleep.

5 & 20	Develop a relaxing bedtime routine. This may include taking a warm bath, reading a book, meditation, or stretching. Avoid stimulating activities right before bedtime, including watching TV or discussing a stressful topic.
6 & 21	Avoid moderate to vigorous exercise at least 2-3 hours before bedtime. Exercising immediately before bedtime stimulates your body and brain, making it hard to fall asleep. There is evidence however that doing regular (preferably moderate to vigorous) exercise improves your sleep at night. Talk to your physical therapist about an appropriate exercise program.

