7 & 22	Avoid caffeinated foods and drinks at least 4 hours before bedtime (includes most tea, coffee, chocolate, and soft drinks). Check the presence of caffeine in your drink or food by reading the label. Caffeine can cause difficulty falling asleep and increase the number of times you wake up during the night.
8 & 23	Refrain from drinking alcohol or smoking at least 3 to 4 hours before bedtime. Although people may think drinking alcohol causes relaxation before bedtime it can actually increase the number of times you wake up during the night and can cause you to wake up early. Nicotine in cigarettes acts as a stimulant that can cause difficulty falling asleep.
9 & 24	Do not take unprescribed or over-the-counter sleeping pills.
10 & 25	Avoid daytime napping so that you are tired at night and can fall asleep easily. If you feel you need to take a nap, limit the nap to 30 minutes and avoid napping in the evening.
11 & 26	Make your sleeping environment comfortable and relaxing. This includes avoiding too much light and disturbing noises. Stop using light emitting electronics (ie, television, computer, smartphone) at least 30 minutes before bedtime as the blue light that is emitted can disrupt sleep by suppressing melatonin production. Use ear plugs, light-blocking curtains, or an eye mask if needed.
12 & 27	Keep the temperature comfortable. Being too warm or cold may disturb your sleep. Also, use a comfortable and supportive pillow and mattress.
13 & 28	Avoid eating a large meal or spicy food 2-3 hours before going to bed. Your digestive system slows down while you are sleeping, which can stimulate acid secretions that cause heartburn. A light snack may be helpful if you are hungry. Avoid excessive liquid 2-3 hours before bedtime.
14 & 29	Eat nutritious, well balanced meals. Avoid eating a large amount of highly processed and sugary foods as these can disrupt the hormones that help regulate your sleep patterns. Instead try to make a habit of eating whole foods whenever possible.
15 & 30	Talk to your doctor or health professional if you still have trouble sleeping.

Table 2: Sleep hygiene tips that will be sent out through text messaging

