## Data Analysis

Statistical analyses will begin with the collection and reporting of demographic information for all study participants. This information will provide context for the sample and allow for appropriate interpretation of study outcomes.

Pre- and post-intervention survey data will be analyzed using paired-sample t tests. This approach will compare participant scores from the surveys administered at the beginning of the study to scores from the same surveys administered at the conclusion of the study, allowing for assessment of within-subject changes over time.

In addition to survey measures, objective sleep tracker data will be analyzed using paired-sample t tests. This will allow for comparison of baseline sleep measures with post-intervention measures, providing an additional source of quantitative evidence regarding the impact of the intervention.

All statistical analyses will be conducted using appropriate statistical software, and significance will be set at  $p < .05$ .

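### Aim 2 speaks of more sustainable results, but the SAP has no between-arm test or use of the 4-week time course, and nothing is measured after the texts stop

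*Protocol*

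**What the plan says.** **Intent.** The rationale under Protocol, Specific Aim 2 says "we want to test if longer-term reminders outside the initial training would provide even more sustainable results". The formal hypothesis in the same paragraph is narrower and has no time horizon: "We hypothesize that automated text messaging will enhance the treatment effect of a one-time educational session on sleep health in CDOA".

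**Schedule.** In the Aim 2 experimental design, "The participants will receive the text messages for a total of 4 weeks". The outcome visit comes next: "Following the 4 weeks, PI and student researcher(s) will meet again with all participants". There is no other visit after baseline: "Each participant will have a total of 2 sessions to complete". The protocol's opening design section has the tracker worn for 2 baseline weeks and 4 weeks after the intervention.

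**Analysis.** SAP, Data Analysis, compares surveys before and after with paired t tests and adds that "objective sleep tracker data will be analyzed using paired-sample t tests", baseline against post-intervention. It names no comparison between arms and no weekly or trend analysis. The protocol instead names a 2x2 mixed ANOVA of pre/post measurements, although there are three groups. Table 1 defines the tracker domains as averages (a standard deviation for regularity), without saying over which nights.

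**The concern.** Whether reminders help an effect last is a question about its course over time, compared between the two education arms. The SAP's tests use neither element. A paired t test reduces each participant to one value before and one after, and it looks for change within participants. Change in the text arm, even beside a non-significant change in the video arm, does not show that the arms differ. It also cannot be separated from what would have happened anyway, such as the effect of wearing a tracker.

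At stake is the Aim 2 conclusion. A significant pre/post change could be reported as evidence that texts enhance or sustain the benefit of the video when neither was tested. Meanwhile the nightly tracker records, which could show whether the video effect fades without reminders, would go unused.

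**Working it through.** **1. Timeline.** The plan's own figures agree: 2 + 4 = 6 weeks of tracker wear, and 3 x 40 = 120 participants. Time observed after the last text is 42 - (14 + 28) = 0 days. Table 2 lists texts up to day 30, which would make it 42 - (14 + 30) = -2 days. The 28 and 30 days need reconciling, but neither leaves a text-free window.

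**2. What the planned tests estimate.** Paired t test: mean of (post - baseline) within participants. The Aim 2 hypothesis: mean (post - baseline) under text-plus-video, minus the same under video alone. The second quantity does not appear in the SAP.

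**3. What a single post value can hide.** Assume that post means the average of all 28 nights. Take three effects over nights t = 0 to 27: flat at 1; fading as 2(1 - t/27); growing as 2t/27.

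| Effect | 28-night mean | First week | Last week |
|---|---|---|---|
| Flat | 1.00 | 1.00 | 1.00 |
| Fading | 1.00 | 1.78 | 0.22 |
| Growing | 1.00 | 0.22 | 1.78 |

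For example, the fading last week is 2(1 - 24/27) = 0.22. The three patterns give the same pre/post result.

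**4. The same point as a gap between the education arms.** Suppose the video-only effect halves every H days and texts hold it constant. The gap, as a share of the initial effect, is 1 minus the mean of 2^(-t/H) over the window. For H = 14 in week 1: 1 - (1 - 2^(-0.5))/(0.5 ln 2) = 1 - 0.845 = 0.155 (0.1549 before rounding, so 15%).

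| H (assumed) | Week 1 | Week 4 | All 28 days |
|---|---|---|---|
| 7 days | 28% | 91% | 66% |
| 14 days | 15% | 70% | 46% |
| 28 days | 8% | 45% | 28% |

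The half-lives are not in the documents. If the post value were taken from the final week alone, the week-4 column would apply and the dilution would disappear, but a lasting effect would still look the same as a constant extra benefit.

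**5. Which outcomes can be followed weekly.** The tracker domains can. The 0-6 composite cannot, because its alertness component (Epworth) is collected only at the two visits.

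**6. Precision.** The documents give no effect size, SD or power. For a simple two-arm comparison with 40 per arm, assuming two-sided alpha 0.05 and 80% power, the detectable difference is (1.960 + 0.842) x sqrt(2/40) = 0.63 SD. Power is 61% at 0.5 SD and 27% at 0.3 SD. No power can be given for the weekly trend without the within-person correlation.

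**The case against.** The strongest reply is that the mention of sustainability is motivation only. The stated aim and hypothesis concern augmentation, and softening one phrase would remove the mismatch. That stands, and it is why the fix includes the wording.

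Second, the design does carry information on maintenance. The video arm receives nothing further for 4 weeks, and both education arms are assessed at week 6, so there is a randomised comparison 4 weeks after education, with and without reminders. That also stands. A reader might infer that the trial is incapable of saying anything about persistence, and the documents do not support that. The gap within the texting period lies in the analysis; only persistence after the last text lies outside the design.

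Third, a reader might infer that the SAP commits to averaging all 28 nights and so discards the weekly data. It does not say so: the post-intervention window is undefined, and a final-week average would fit the text equally well. The dilution in the 28-day column is therefore conditional.

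Fourth, the protocol's mixed ANOVA has a between-group factor, so a group-by-time test might be intended. But a 2x2 layout does not fit three groups, the protocol does not say which two would be compared, and the SAP does not carry the test forward.

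Finally, weekly modelling covers the tracker outcomes only and will be imprecise. This argues for a supporting role and against making the week-4 contrast and trend the sole test of Aim 2.

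**Conclusion.** The point holds in a limited form. On the text available, the SAP tests neither the added effect of texts over the video nor the better maintenance of that effect during the 4 weeks, and with 0 text-free days the trial cannot address durability once texts end. The formal hypothesis itself needs only the first of these, so the missing between-arm contrast is the main defect and the unused time course is secondary.

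The size of the loss cannot be derived from the documents. The tables above rest on assumed effect shapes and half-lives, and the all-nights figures also assume a 28-night window; they show that the patterns cannot be told apart, not how large the effect is in this trial. No stated sample-size figure is shown to be wrong. The study-design figures and part of the SAP were not available, so the absence of a trend analysis or arm contrast is judged on the remaining text.

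**What to change.** 1. In the SAP, make the Aim 2 test a baseline-adjusted contrast of text-plus-video versus video on the end-of-study outcome, with an estimate and confidence interval. Align the protocol's ANOVA wording with it.
2. Define the nights that make up the post-intervention value.
3. Prespecify, as a supporting analysis of the continuous tracker outcomes (not the 0-6 composite), a repeated-measures model with arm, week (1-4), arm-by-week and baseline. Report the week-4 contrast and the trend with confidence intervals.
4. Limit the Aim 2 conclusion to effects during the 4 weeks of texting, and reword the rationale so that it makes no claim about durability after texts end.
5. Reconcile the 4-week texting period with the 30 days in Table 2.

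The cost is wording and a little more analysis, with no new visits, data or staff. The drawback is an imprecise trend estimate with 40 per arm, which should be presented as such.

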Study Protocol

Effects of Sleep hygiene Education on Sleep Health in Adults Ages 50 -80

[name]

Updated: 09/02/2024

NCT: 06129045

Approved by human subject protection review board committee on 09/02/2024

Experimental design: The two-year randomized control trial will begin in the fall (September 2023) and conclude before the end of the academic year (May 2025). The principal investigator and student researcher(s) will recruit participants through flyers and word of mouth. Flyers will be placed at senior centers, community centers, and medical centers in Rapid City, SD. Interested participants will email or call [name] to enroll in the study. [name] will meet with the participant to determine the eligibility status for the study. Due to the use of human subjects in this study, the research protocol will be approved by the University of South Dakota, Black Hills State University institutional review boards, and the National Institutes of Health before participant recruitment. Participant inclusion criteria will include participants ages 50-80, who own a smartphone with the capability of receiving text messages. Exclusion criteria: an untreated diagnosed sleep disorder such as insomnia or obstructive sleep apnea, and inability to wear any sleep tracking device on their wrist. During the initial visit, participants will read through and sign informed consent explaining the procedures and expectations of them during the study. The participants will then complete the following questionnaires related to the primary objectives of the study: the Ru-SATED questionnaire which includes the Sleep Diary (based on the Consensus Sleep Diary) and Epworth Sleepiness Scale, Pittsburgh Sleep Quality Index, and the Sleep Hygiene Index. Participants will also complete the Perceived Stress Scale, and the Numeric Pain Rating Scale as secondary outcomes. Initial data collection will consist of taking anthropometric measurements and vital signs, with the assistance of the student researcher. The anthropometric measurements will include the following: body weight, height, and body mass index (BMI). BMI will be calculated by the standard method (body weight [kg]/ height [m]2) from weight and height measurements. The vital signs assessed will be resting blood pressure, heart rate, and respiratory rate. Following anthropometric data collection and vital signs, the participants will be instructed on the use of the wearable sleep tracker and assisted with setting up and charging the device. Participants will be instructed to contact the PI with any questions throughout the study by email or phone.

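### Randomisation appears to come before the 2-week tracker baseline, and the visible text neither withholds the arm during those weeks nor describes a contact at week 2

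*Protocol*

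**What the plan says.** The timing has to be pieced together from two protocol sections and the SAP.

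- **Assignment** (Protocol, Specific Aim 2, Experimental design): "Following anthropometric data collection and vital signs, the participants will be randomly assigned to one of three groups (Figure 2"). No day or visit is named.
- **Tracker set-up** (Protocol, opening Experimental design section, describing the initial visit): "Following anthropometric data collection and vital signs, the participants will be instructed on the use of the wearable sleep tracker".
- **Wear period** (same section): after the initial meeting, all participants "wear the sleep tracker on their wrist for 2 weeks to collect preliminary data and then 4 additional weeks following their intervention", 6 weeks in all.
- **Sessions** (Specific Aim 2): "Each participant will have a total of 2 sessions to complete". The second is fixed in the opening section: "At the end of the 6-week study period, the PI and/or student researcher(s) will again meet with each participant".
- **Use of the baseline** (SAP, Data Analysis): paired tests on tracker data for "comparison of baseline sleep measures with post-intervention measures". The protocol also compares pre and post measurements.

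The video is to be watched once by two of the three groups. No day, place or route is given in the visible text. Nor does the visible text say that participants or staff are kept unaware of the arm at any stage.

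**The concern.** Allocating early does not by itself bias anything. What matters is whether participants know their arm while the baseline is being recorded. In this trial one arm gets nothing, one a video, and one a video plus daily texts, so the arm cannot be hidden once treatment starts. It can be hidden before then, and the visible text does not say that it is.

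Someone told at week 0 that they are in a sleep-education arm, and given a wrist tracker the same day, may start to pay attention to sleep at once. Someone told they are a control may lose interest, or may look for advice elsewhere. Either would make the first 2 weeks of tracker data something other than a pre-intervention measure, and possibly a different thing in each arm. Every planned pre/post comparison of tracker data uses those nights, and a baseline affected in this way cannot be recorded again later.

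**Working it through.** **The plan's own figures.** Tracker wear: 2 + 4 = 6 weeks, as stated. Sample: 3 × 40 = 120, as stated. Nothing here needs correcting.

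**Order of events, from the visible text.**

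1. Assignment follows the anthropometric and vital-sign measurements (Specific Aim 2).
2. Those measurements are taken at the initial visit (opening section). Tracker set-up at that visit is introduced by the same opening clause as assignment.
3. The same measurements are next taken at the closing meeting, after treatment, so they cannot be the ones that precede assignment.
4. The 2-week tracker baseline starts after the initial meeting.
5. Only two sessions exist, at week 0 and at the end of week 6, so no session is available at week 2 for allocation.

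Steps 1 to 5 point to assignment at the initial visit, before baseline night 1. This is an inference: *following* sets an earliest time, not a day, and a remote assignment at week 2 is not excluded.

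**Where the sections do not meet.** The opening section puts the intervention between the 2 weeks and the 4 weeks. The Aim 2 section goes from assignment to 4 weeks of texts to the final meeting and does not mention the run-in. Taken with the 6-week total, the texts occupy the last 4 weeks (6 − 4 = 2 weeks before them). Neither section describes a contact at the end of week 2 at which an arm could be disclosed or a video supplied.

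**What depends on the run-in nights.**

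- Baseline nights: 2 × 7 = 14. Total nights: 6 × 7 = 42. Share: 14/42 = 33%. These 14 nights are the whole tracker baseline.
- Composite domains with the tracker as source (Table 1): Regularity, Timing, Efficiency and Duration, so 4 of 6.
- Alertness comes from the Epworth scale, completed at the initial visit as part of "the Ru-SATED questionnaire which includes the Sleep Diary (based on the Consensus Sleep Diary) and Epworth Sleepiness Scale". The opening section describes the questionnaires before the measurements that precede assignment, so its baseline is not shown to be affected.
- Satisfaction comes from the diary: "Satisfaction will be operationalized as the average" restedness score. The recording window is not stated, so it would be a fifth domain only if the diary covers run-in nights.

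The documents give no figure from which the effect of knowing one's arm could be sized.

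**The case against.** The strongest reply is that the missing facts may not be missing. Figures 1 and 2 are both captioned as study designs, the assignment sentence itself points to Figure 2, and neither figure could be seen. Part of the SAP was also unavailable. Any of these may give the day of assignment, disclosure and viewing. This stands, and it is why the point is limited to the visible text.

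A second reply is that the opening section already gives the sequence: 2 weeks of preliminary data, then the intervention, then 4 weeks. That also stands as far as it goes. With that sequence in view, the SAP's baseline plainly means the first 2 weeks, and a definition of baseline nights is only a cross-reference to add. But a position for the intervention does not say when participants learn their arm, and it leaves unexplained how a video reaches them when no session falls at that time.

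A reader might go further and infer that the video is shown at the initial visit, so that the education itself contaminates the baseline. The documents do not support this: the protocol's stated order puts the intervention after the 2 weeks. Nor can the four tracker domains be called exposed as a matter of fact. What is certain is that they rely on the run-in nights. Exposure depends on a disclosure during those weeks that the visible text neither describes nor rules out.

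**Conclusion.** The concern holds in a limited form. On the natural reading, randomisation comes before the tracker baseline, in a trial whose participants cannot be blinded once treated, with no withholding of the arm and no week-2 contact described. At stake is the only tracker baseline: 14 nights, on which four of the six composite domains rest. The size and direction of any distortion are unknown, and it is nil if disclosure comes after the run-in.

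The conclusion rests on two assumptions: that assignment takes place at the initial visit, and that participants may be told their arm then. The unseen figures or SAP text could overturn either. The point goes beyond a request for missing detail because delaying disclosure is a specific and cheap protection for the whole tracker baseline. It is a change that should be made, held with medium confidence. It is not evidence that the baseline has been compromised.

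**What to change.** Reconcile the opening Experimental design section with the Specific Aim 2 design so that they agree on when assignment, disclosure and the video occur. Then do one of two things: randomise after the last baseline night, or randomise at the initial visit and keep the allocation undisclosed until that night has passed. The video would follow in the order the protocol already implies. If the figures or the rest of the SAP already provide for this, repeating it in the text is enough.

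For participants already enrolled, report by arm how many knew their arm during the baseline nights. This is likely to be needed, since the protocol is dated 09/02/2024 and the trial runs from September 2023 to May 2025.

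Two small additions to the text would help: a line in the SAP naming the baseline nights, and a statement of the diary's recording window.

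The cost is protocol and SAP wording plus one remote contact per participant at the end of the run-in (up to 120), with no extra visit. If the change is made mid-trial, two procedures must be reported, and undisclosed baseline nights cannot be recovered for those who already knew their arm.
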